### 5.2 Exclusion criteria

Patients eligible for this study must not meet **any** of the following criteria:

- 1. Has an oncogenic *KRAS* mutation.
- 2. Has received any anti-cancer treatment including hormonal and investigational agents within 21 days prior to first dose of bimiralisib.
- 3. Patients who receive gamma knife radiosurgery for brain metastases or whole brain radiation are eligible if gamma knife radiosurgery was performed > 2 weeks before treatment is started or whole brain radiation was performed > 4 weeks before treatment is started, and are clinically stable.
- 4. Known hypersensitivity to any of the excipients of bimiralisib capsules.
- 5. Major surgery within 28 days prior to first dose of bimiralisib or persisting side effects that have not improved to NCI-CTCAE grade 1 or better.
- 6. Poorly controlled diabetes mellitus, steroid-induced diabetes mellitus, FPG > 150 mg/dl.
- 7. Concomitant treatment with medicinal products that increase the pH (i.e. reduce acidity) of the upper gastrointestinal tract, including, but not limited to, proton-pump inhibitors (e.g. Omeprazole), H2-antagonists (e.g. Ranitidine) and antacids is restricted. Patients may be enrolled in the study after a washout period sufficient to terminate their effect.
- 8. Active tobacco or e-cigarette smoking habit. Non-smoker status will be confirmed by cotinine test at screening in patients with a history of smoking. Additional cotinine tests may be administered at the discretion of the treating investigator if current smoking is suspected.
- 9. Patients who are on (or will require) prolonged systemic corticosteroid treatment during the study (see section 11.1.4).
- 10. Use of oral herbal preparations or medications during the study period. Patient should stop using oral herbal medications 7 days prior to the first dose of bimiralisib
- 11. Concurrent severe and/or uncontrolled medical conditions that would, in the investigator's judgment, contraindicate patient participation in the clinical study or require concomitant anti-cancer drugs (e.g., active or uncontrolled severe infection, chronic active hepatitis, immuno-compromised, acute or chronic pancreatitis, uncontrolled high blood pressure, interstitial lung disease, etc.).
- 12. Has other active malignancies that require systemic treatment.
- 13. Has a known history of HIV infection (testing not mandatory).
- 14. Any of the following cardiac abnormalities:
  - History of, or current, documented congestive heart failure (New York heart association functional classification iii iv), documented cardiomyopathy
  - Symptomatic (NYHA class II or higher) left ventricular ejection fraction (LVEF) < 40% as determined by multiple gated acquisition (MUGA) scan or echocardiogram (echo)
  - Myocardial infarction  $\leq 6$  months prior to enrolment
  - Unstable angina pectoris
  - Serious uncontrolled cardiac arrhythmia
  - Symptomatic pericarditis

- 15. Impaired gastrointestinal (GI) function or GI disease that may significantly alter the absorption of study drug.
- 16. Patient has a history of non-compliance to medical regimen or inability to grant consent.
- 17. Pregnant or nursing (lactating) women.
- 18. Medically documented history of or active major depressive episode, bipolar disorder (i or ii), obsessive-compulsive disorder, schizophrenia, a history of suicidal attempt or ideation, or homicidal ideation (immediate risk of doing harm to others) or ≥ CTCAE grade 3 anxiety
- 19. History of interstitial pneumonitis or patients who require chronic oxygen supplementation.

### 6 IMP supply and handling

### 6.1 Study treatment

Bimiralisib is the investigational medicinal product (IMP) for this trial.

Bimiralisib is manufactured according to current good manufacturing practices (cGMP). Bimiralisib is provided in capsules for oral administration by PIQUR Therapeutics AG, Basel. Each capsule contains 20 or 80 mg of the active study drug substance.

### 6.2 Supply of bimiralisib

PIQUR will order an initial stock of medication for each participating site upon receipt of health authority, local EC and hospital approvals. The distribution will be managed by an authorized distributor.

### 6.3 Packaging and shipment of bimiralisib

The capsules are packaged in bottles with a sealed and child-resistant closure, and should be stored at room temperature ( $15^{\circ}$ C to  $25^{\circ}$ ). The shelf-life and storage conditions will be continually assessed based on accelerated and long-term stability data.

### 6.4 Handling of bimiralisib

The study pharmacist, or a delegated person at the site, will be responsible for handling study drug, preparation of the appropriate doses to be administered, and completion of trial-specific drug accountability logs. However, the investigator will finally be responsible for the accountability of all used and unused clinical trial supplies.

Study drug must be handled strictly in accordance with the protocol and will be stored in a limited access area or in a locked cabinet under appropriate environmental conditions. Study drug should be administered only to patients participating in the study.

### 6.5 Dispensing and accountability of bimiralisib

The site must maintain an overall drug accountability log for the study, as well as individual accountability records for each patient. The dose, amount dispensed, amount received, and amount remaining unused must be recorded in the source document. Drug accountability will be verified by the monitor during site visits and the completion of the study for each individual patient

In order to facilitate drug accountability and monitor compliance, the patient will complete a diary on the intake of bimiralisib which will be brought to the site at each visit. At each visit, the site will make a photocopy of the diary which will be dated and stored with the patient's source data.

### 6.6 Unused bimiralisib

Partly unused or expired medication can only be destroyed at the site after drug accountability has been performed by the monitor and authorization has been given by the sponsor. The destruction should be documented using the drug inventory log.

### 7 **IMP administration**

### 7.1 **IMP dosing instructions**

Patients will be treated with 140 mg bimiralisib p.o. once daily on two consecutive days followed by five days without treatment in consecutive 7-day treatment blocks. Patients will follow this iterative "2d on / 5d off" treatment scheme until unacceptable toxicity, tumor progression, patient's request for withdrawal, investigator judgment or death, whichever comes first.

Bimiralisib should be taken in the morning at the same time on an empty stomach at least 1 hour before breakfast with a full glass of non-carbonated, non-flavored water (~7 ounces or 200ml).

For patients who are unable to swallow bimiralisib capsules, capsule content is to be suspended in non-carbonated, non-flavored water. As for oral capsule administration, bimiralisib suspension is to be administered in the morning on an empty stomach. Bimiralisib suspension may be administered by mouth or through a gastric feeding tube as applicable following standard local practice, including rinsing of the tube with water. Feeding tubes that bypass the stomach (e.g. J tubes) cannot be used for bimiralisib administration. In total, suspension and rinsing volume – by tube or by mouth – should be equivalent to about 7 ounces.

*Exception:* patients who follow the ranitidine mitigation strategy will take bimiralisib in the evening on an empty stomach at least 1 hour before dinner. Patients should be instructed not to

bite or chew on the capsules. In case of breakage of the capsules in the oral cavity, additional water should be taken as a rinse.

Re-dosing is not allowed if the patient vomits after bimiralisib intake.

Should a patient miss drug intake at the scheduled time, the planned dose of bimiralisib may be administered within 12h of delay in the following manner: at least 2 hours after the previous meal and 1 hour before the next meal. In case of longer delay the dose is to be omitted and bimiralisib dosing is to be resumed at the next scheduled day.

At specified clinic visits (Table 2), the study drug will be administered in the clinic with dosing appropriately timed relative to blood sampling for bimiralisib pharmacokinetics. On these days the patient comes to the clinic fasted and should refrain from taking food until the collection of the post-dose PK sample.

### 7.2 Treatment interruptions and bimiralisib dose reductions

For patients who do not tolerate the protocol-specified dose, dose adjustments are permitted in order to allow the patient to continue bimiralisib treatment. Changes in dosing schedule are not allowed. Any changes in bimiralisib administration must be recorded on the CRF. Whenever possible, any dose adjustment of bimiralisib should be discussed between the investigator and the study sponsor prior to implementation.

As a first step to manage bimiralisib-related toxicities, bimiralisib treatment should be temporarily interrupted.

All treatment interruptions, discontinuations and dose reductions must be based on the worst preceding AE as graded by the NCI common terminology criteria for AE (NCI-CTCAE version 5.0). Once the bimiralisib dose has been reduced, re-escalation is not permitted.

Guidelines for treatment interruptions and bimiralisib dose reductions are described in Table 4.

## Table 4: Treatment interruptions and dose reductions for adverse events (except hyperglycaemia) considered related to bimiralisib by the treating physician

Reason	Treatment change
Non-haematological AE Grade 4	Stop bimiralisib treatment permanently.
Haematological AE Grade 4	Interrupt bimiralisib treatment. If AE resolves to baseline or CTCAE grade 1 within 7 days, patients may resume treatment at the reduced dose of 100mg. If AE resolves within 8 to 14 days, patient may resume treatment at the reduced dose of 100mg if agreed between investigator and sponsor. If AE does not resolve to baseline or CTCAE grade 1 within 14 days, bimiralisib treatment must be discontinued permanently.
Grade 3 AE	Interrupt bimiralisib treatment. If AE resolves to baseline or CTCAE grade 1 within 7 days, patient may resume treatment at 140mg. If AE resolves to CTCAE grade 1 within 8 to 14 days, patient may resume treatment at the reduced dose of 100mg. If AE does not resolve to baseline or CTCAE grade 1 within 14 days, bimiralisib treatment must be discontinued permanently.
Any non-haematological AE grade 2	Continue bimiralisib treatment. Dose reduction at the discretion of the treating physician

Patients who after dose interruption do not tolerate bimiralisib treatment at 100 mg must be permanently discontinued. If during the first three months on study, a patient cannot restart at the 100 mg dose level within 14 days, this patient is not evaluable for the primary endpoint, and the investigator must discuss the individual benefit-risk evaluation of this patient with the sponsor before restarting dosing. These patients may be replaced.

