	
 
SAEs resulting in death
 

	
 
SAEs resulting in discontinuation
 

	• SAEs resulting in dose reduction or dose interruption
	• Frequency, time to onset and severity of AEs
	• Changes from baseline in safety parameters
	
 
Additional Efficacy: TTR, DOR, TTF and PFS, evaluated according to the response evaluation criteria in solid tumors (RECIST), version 1.1 [2, 3]
 
Pharmacokinetics: Bimiralisib plasma concentrations. To be reported separately.
 

F _1_4	
Exploratory	• ctDNA:
endpoints	
 
ctDNA sequences and levels in patient plasma
 

	Pre-cancerous keratinocytic skin lesions:
	• Number and size of index lesions
	NOTCH protein levels
	
 
Protein levels
 
Protein levels of cleaved NOTCH1 (NICD) as determined by immunohistochemistry (IHC)
 

Version 5.0

Study design	This is an open-label, single arm, two-stage study to evaluate the efficacy and safety of bimiralisib in patients with r/m HNSCC containing NOTCH1 LOF mutations. The study will be conducted in $1 - 4$ centers. Patients will be treated with 140 mg bimiralisib p.o. once daily on two consecutive days followed by five days without treatment in consecutive 7-day treatment blocks. Patients will follow this iterative "2d on / 5d off" treatment scheme until unacceptable toxicity, tumor progression, patient's request for withdrawal, investigator judgment or death, whichever comes first.
	Stage 1 of the study will enroll 10 patients. Response evaluation of Stage 1 patients will be performed in an ongoing manner (ongoing analysis, OA). If two or more patients in stage 1 show a confirmed partial or confirmed complete response, stage 2 may enroll 19 patients. If less than two patients in stage 1 show a confirmed partial or confirmed complete response during the OA, a formal futility analysis will be performed once all 10 patients in Stage 1 have been assessed for their response to bimiralisib. If futility is confirmed as per defined criteria, the study will be stopped.
	The study will end when all patients have been treated for 6 months or have discontinued study participation for any reason, whichever comes first.
Patient population	Adult patients with recurrent or metastatic HNSCC with NOTCH1 LOF mutations

Inclusion criteria	Patients may be included in the study if they meet all the below inclusion criteria:

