	
 
13. Has a known history of HIV infection (testing not mandatory).
 
14. Any of the following cardiac abnormalities: 
 
History of, or current, documented congestive heart failure (New York heart association functional classification iii - iv), documented cardiomyopathy
 
Symptomatic (NYHA class II or higher) left ventricular ejection fraction (LVEF) < 40% as determined by multiple gated acquisition (MUGA) scan or echocardiogram (echo)
 
Myocardial infarction ≤ 6 months prior to enrolment
 
Unstable angina pectoris
 
Serious uncontrolled cardiac arrhythmia
 
Symptomatic pericarditis
 
 
 
15. Impaired gastrointestinal (GI) function or GI disease that may significantly alter the absorption of study drug.
 
16. Patient has a history of non-compliance to medical regimen or inability to grant consent.
 
17. Pregnant or nursing (lactating) women.
 
18. Medically documented history of an active major depressive episode, bipolar disorder (I or II), obsessive-compulsive disorder, schizophrenia, a history of suicidal attempt or ideation, or homicidal ideation (immediate risk of doing harm to others) or ≥ CTCAE grade 3 anxiety
 
19. History of interstitial pneumonitis or patients who require chronic oxygen supplementation.
 

Investigational therapy	140mg bimiralisib (capsules of 20mg and 80mg, supplier PIQUR Therapeutics AG, Basel, Switzerland) p.o. once daily on two consecutive days followed by five days without treatment in consecutive 7-day treatment blocks. Patients will follow this iterative "2d on / 5d off" treatment scheme until unacceptable toxicity, disease progression, patient's request for withdrawal, investigator judgment or death, whichever comes first.
Efficacy assessments	Radiological tumor assessments will be performed by CT or MRI according to a standard protocol at baseline (BL), every 6 weeks, and at the end of treatment (EOT). PET scans are not permitted for efficacy assessment. All reasonable effort should be made for radiological tumor assessments at a study site to be performed by the same person. ORR, TTR, DOR, TTF and PFS will be determined according to RECIST version 1.1 [2, 3].

Version 5.0

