### 4 Study design

### 4.1 Overall design

This is an open-label, single arm, two-stage study to evaluate the efficacy and safety of bimiralisib in patients with r/m HNSCC containing *NOTCH1* LOF mutations. The study will be conducted in 1 - 4 centers.

Patients will be treated with 140 mg bimiralisib p.o. once daily on two consecutive days followed by 5 days without treatment in consecutive 7-day treatment blocks. Patients will continue this iterative "2d on / 5d off" treatment scheme until unacceptable toxicity, tumor progression, patient's request for withdrawal, investigator judgment or death, whichever comes first. The bimiralisib dose may be decreased to 100 mg p.o. administered on the same dosing schedule in order to manage safety and/or tolerability (see section on dose interruptions and modifications, section 7.2). Changes in dosing schedule are not allowed.

Stage 1 of the study will enroll 10 patients. Response evaluation of Stage 1 patients will be performed in an ongoing manner (ongoing analysis, OA). If two or more patients in stage 1 show a confirmed partial or confirmed complete response, Stage 2 may enroll 19 patients. Conversely, Stage 2 may not start if only one or no patients in Stage 1 have shown a confirmed partial or confirmed complete response.

If patients withdraw consent or drop out for other reasons unrelated to safety or disease progression, they may be replaced. This includes patients who start smoking (as evidenced by cotinine test) within the first 12 weeks on bimiralisib treatment, because smoking is known to severely compromise bimiralisib exposure due to induction of CYP1A2, the main metabolizing enzyme of bimiralisib. These patients may remain on treatment but will be replaced. Patients for whom IHC analyses indicated high protein levels of NICD which are deemed incompatible with NOTCH1 loss-of-function may be replaced. In total, we anticipate up to 20% of patients to drop out, resulting in enrollment of up to 35 patients in total.

The study will end when all patients have been treated for at least 6 months or have discontinued study participation for any reason, whichever comes first.

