# 9.3 Efficacy assessments

Radiological tumor assessments will be performed by CT or MRI according to a standard protocol at baseline (BL), every 6 weeks ( $\pm$  3 days) until disease progression, starting of another anti-neoplastic treatment, or death whichever occurs first.

Response evaluation criteria in solid tumors (RECIST), version 1.1, will serve to evaluate responses to bimiralisib treatment.

For the futility analysis, only a confirmed partial response (PR) or confirmed complete response (CR) are considered a response to treatment.

Confirmation of a treatment response requires at least two on-treatment response assessments. As per protocol, the first two on-treatment response assessments are scheduled for day 43 (+/-3 days) and day 85 (+/-3 days), respectively. If a treatment response in a patient does not meet the RECIST criteria for a partial response at the first response assessment, confirmation of a potential response might occur only at subsequent later on-treatment response assessments

PET scans are not permitted for efficacy assessment. If a patient has undergone radiological tumor assessment prior to consenting to the study, the data may be used as the baseline assessment if the imaging protocol is in line with the standard imaging protocol of the study and if the assessment was performed within 28 days of receiving the first dose of bimiralisib.

All reasonable effort should be made for radiological imaging used for tumor assessments to be read by one dedicated local radiologist at each study center. Results must be reported in the CRF. ORR, TTR, DOR, TTF and PFS will be determined according to the response evaluation criteria in solid tumors (RECIST), version 1.1 [2].

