# **10.2** Sample size determination

To minimize accrual if bimiralisib is ineffective, a Simon's optimal two-stage design is used. In order to have 80% power to detect a response rate of 30%, (one-sided  $\alpha$ =0.05 and  $\beta$ =0.20) up to 10 patients will be enrolled in the first stage. If 1 or 0 patient respond to the treatment, the trial will be closed due to futility and the treatment is considered ineffective. If two or more patients have an objective response, the study will enroll an additional 19 patients in the second stage. The null hypothesis (H0: ORR  $\leq$  10%) will be rejected if the number of responses is  $\geq$  6 in 29 patients.

If patients withdraw consent or drop out for other reasons unrelated to safety or disease progression, they may be replaced (see section 9.11). We anticipate up to 20% of patients to drop out, resulting in enrollment of up to 35 patients in total.

This sample size is also reasonable to evaluate the pharmacokinetic and other correlative science endpoints; yet, no explicit sample size justification is made for these exploratory endpoints.

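### Section 7.2 drops early toxicity failures from the ORR and lets them be replaced, against 4.1, 9.11, 10.2 and SAP 1.2

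*Protocol*

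**What the plan says.** **Section 7.2, text below Table 4.** The rule covers early cases, up to month three, and reads: "a patient cannot restart at the 100 mg dose level within 14 days, this patient is not evaluable for the primary endpoint". It then adds: "These patients may be replaced". The table above concerns adverse events judged related to bimiralisib, so this is removal for toxicity.

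**Replacement elsewhere.** Section 4.1 states: "If patients withdraw consent or drop out for other reasons unrelated to safety or disease progression, they may be replaced". Section 9.11, the dedicated replacement section, has the same sentence, and so do 10.2 and SAP 1.2. Sections 4.1 and 9.11 add two further cases, patients who start smoking in the first 12 weeks and patients with high NICD. Neither mentions toxicity.

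**Analysis set.** Section 10.4.1 puts all efficacy analyses on the per-protocol set (PPS). The synopsis defines it as all patients treated per protocol. Section 10.3.2 leaves the exclusions to the SAP and a data handling plan. The SAP text available (1.1 and 1.2) lists none.

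**Design.** Section 10.2 requires at least 2 responders in 10 to continue and at least 6 in 29 to reject an ORR of 10% or less. On enrolment it says: "We anticipate up to 20% of patients to drop out, resulting in enrollment of up to 35 patients in total". The synopsis says that, with fewer than two responders, "a formal futility analysis will be performed once all 10 patients in Stage 1 have been assessed for their response to bimiralisib".

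**Response.** Section 9.3 says: "Confirmation of a treatment response requires at least two on-treatment response assessments". The first two are scheduled for Day 43 and Day 85. The synopsis also plans a scan at end of treatment.

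**The concern.** Two statisticians could build different denominators for the primary endpoint from this text. Under 9.11 a patient lost to toxicity is not replaced. Under 7.2 the same patient leaves the ORR and the place may be refilled. On a literal reading of the synopsis, someone stopped exactly as Table 4 requires was treated per protocol and stays in the PPS, yet 7.2 takes that patient out.

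The direction is predictable. A patient who fails on toxicity in the first three months will seldom have had both scans needed for confirmation, so removal mostly takes out non-responders. What remains is the ORR among patients who tolerate the drug.

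The stage 1 decision shows what is at stake. Under 10.2, one responder among the first 10 treated closes the trial. If one of the other nine was removed for toxicity and refilled, an eleventh patient can supply the second response. Refilling is optional, and under 12.1.8 the sponsor and principal investigator, with a physician not directly involved in the trial, review tumour response at least every two months. The choice can therefore be made with responses known. If the place is not refilled, fewer than 10 or 29 patients count, and no boundary is given for that.

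**Working it through.** **Inputs.** From 10.1, 10.2 and SAP 1.2: null 10%, target 30%, one-sided alpha 0.05, power 80%, n1 = 10 (continue at 2 or more), n = 29 (reject at 6 or more), up to 35 enrolled. The removal rate q is not in the documents and is assumed to be 3%, 5%, 10% or 20%. The top value borrows the 20% dropout allowance as a ceiling; that allowance is not a toxicity estimate.

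**1. The plan's own figures.** P(reject | p) = Σ over x = 2..10 of P(X1 = x) × P(X2 ≥ 6 − x), with X1 ~ Bin(10, p) and X2 ~ Bin(19, p).

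- p = 0.10: 0.0471
- p = 0.30: 0.8051
- P(pass stage 1 | 0.10) = 0.2639

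The stated design is reproduced.

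**2. Removal without refilling.** If those removed are non-responders, the response count is unchanged, so the chance of meeting the count rules stays at 0.0471 under a 10% ORR. Only the percentage moves: with 5 responders in 29 and three non-responders removed, 5/29 = 17.2% becomes 5/26 = 19.2%.

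**3. Removal with refilling.** Each enrolled patient is removed with probability q, and the true ORR in all treated patients is 10%. The rate among evaluable patients is then

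- 0.10/(1 − q) if none of those removed responds;
- 0.10/(1 − q/2) if they respond at half the rate of the others, since 0.10 = (1 − q)r + q(r/2).

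Patients are enrolled until 10 and then 29 are evaluable, or until the enrolment limit. Six or more responses are still required. For example, with q = 0.10 and no responders removed, the evaluable rate is 0.10/0.90 = 0.111. Exact results:

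| Type I error at all-treated ORR 10% | q = 3% | 5% | 10% | 20% |
|---|---|---|---|---|
| No responders removed, limit 35 | 0.0532 | 0.0577 | 0.0706 | 0.0948 |
| No responders removed, no limit | 0.0532 | 0.0578 | 0.0712 | 0.1099 |
| No responders removed, limit 32 (3 of 6 spare places) | 0.0531 | 0.0571 | 0.0658 | 0.0759 |
| Half rate, limit 35 | 0.0500 | 0.0521 | 0.0572 | 0.0607 |
| P(pass stage 1), no responders removed | 0.2759 | 0.2843 | 0.3071 | 0.3611 |

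At equal response rates the evaluable rate stays at 10% and there is no inflation.

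**4. Reported estimate with refilling.** Six responders with three patients removed and refilled is reported as 6/29 = 20.7%. Among all treated it is 6/32 = 18.8%.

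**5. Fewer than 29 evaluable.** With 35 enrolled, the probability of this is 0.0001 / 0.0015 / 0.0552 / 0.5672 at the four values of q. With 26 evaluable, keeping 6 or more gives alpha 0.0321 and power 0.7612; lowering the rule to 5 or more gives alpha 0.0794. The plan does not say which applies.

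**The case against.** **The null may be meant for evaluable patients.** Efficacy is analysed on the PPS. If the 10% null is the ORR in that set, refilling does not inflate the error: with a limit of 35 it is 4.7% at 3%, 5% and 10% removed and 4.0% at 20%. This is a fair reading, and the inflation above does depend on taking 10% as the ORR in all treated patients. But the plan does not say which population its 10% and 30% describe, and on this reading the trial tests a drug only in those who tolerate it.

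**The size rests on assumptions.** This stands. The largest figures need no response among those removed and toxicity using the whole replacement allowance, which other dropouts, smokers and high-NICD cases share. Combining the half rate with a limit of 32 gives 5.0% / 5.2% / 5.3% / 4.8%, close to nominal. The affected group may also be small: Table 4 excludes hyperglycaemia, and it is unclear whether the 14-day sentence reaches events for which the table stops treatment outright.

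**The text may not conflict.** Section 7.2 can be read as one of the PPS exclusions that 10.3.2 foresees, the other sections do not say that their list is exhaustive, and PPS rules may sit in text not available here. That softens the evaluability point. It does not explain why four passages, the dedicated replacement section among them, carve out safety while 7.2 allows replacement for it.

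**The end-of-treatment scan cannot confirm a response in someone stopped before Day 43.** True. It shows only that such a patient need not be unassessed; without confirmation the patient is a non-responder.

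**A late case could cut the other way.** Removing a patient confirmed at Day 85 would lower the ORR (6/29 = 20.7% to 5/28 = 17.9%), but the window for that is narrow.

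**Conclusion.** The concern holds: the plan is wrong as written and must be corrected. The conflict over replacement is in the current text, by clear implication of the safety carve-out, and nothing available resolves who counts in the primary denominator. The direction follows from the protocol's own scan schedule.

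The size is less certain. It depends on an assumed removal rate, on how those removed would have responded, on how many places are refilled, and on reading the 10% null as the ORR in all treated patients. Under those assumptions about 3% removed, roughly one patient in 29, is enough to pass the nominal 0.05 when none of those removed responds. Under the milder assumptions together the effect is negligible. The case for correction rests on the undefined denominator and the optional refilling with responses in view, more than on any single figure.

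**What to change.** 1. In 7.2, delete the non-evaluability clause and the replacement sentence for toxicity cases, so that replacement follows 9.11 alone.
2. In 10.3, 10.4.1 and the SAP, state that treated patients who stop or cannot restart because of toxicity stay in the 10 and the 29: responders if a CR or PR is confirmed under 9.3, otherwise non-responders.
3. State that such a patient counts as assessed for the stage 1 decision, and give the decision rule if fewer than 29 patients count.
4. Report the ORR in all treated patients as well, because the non-safety replacements under 9.11 can leave a similar bias. Keep the PPS as a sensitivity analysis.
5. Reconcile Table 4, which requires permanent discontinuation after 14 days without resolution, with the sentence below it that contemplates restarting. Likewise reconcile the 14-day sentence with the 21-day hyperglycaemia windows in 12.6.1.1. Evaluability should not depend on which passage is followed; no clinical rule is proposed here.

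**Cost.** Protocol and SAP wording, fewer refilled places, and possibly a slightly lower reported ORR. With these patients kept in and not replaced, the design keeps alpha 0.0471 and power 0.805 for the ORR in all treated patients. If 30% was meant for evaluable patients only, the all-treated target is 0.30(1 − q), and power falls to 78.2% / 76.6% / 72.0% / 66.8% / 61.0% at 3% / 5% / 10% / 15% / 20% removed. In that case the sponsor should restate the power and reconsider the sample size.
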